8.2.5.3 Summaries of Baseline Characteristics, Demographics, and Other Analyses

8.2.5.3.1 Demographic and Baseline Characteristics

Baseline characteristics will be assessed by the use of tables and/or graphs for each cohort. No statistical hypothesis tests will be performed on these characteristics. The number and percentage of subjects screened, treated, primary reasons for screening failure, and discontinuation will be displayed. Demographic variables (e.g., age, region), baseline characteristics, primary and secondary diagnoses, and prior and concomitant therapies will be summarized by cohort either by descriptive statistics or categorical tables.

8.2.6 Multiplicity

This is an estimation study. The estimation of ORR and associated 95% confidence intervals of ORR will be provided. No multiplicity adjustment will be applied in subjects with PD-L1 (+) mTNBC of Cohorts A, overall population (all comers) of Cohort A and in subjects with PD-L1 strong (+) mTNBC.

There are also no hypotheses for other parameters of DOR, DCR, PFS, and OS or for Cohort B.

	17	15.5%	(9.8,23.5)
	18	16.4%	(10.5, 24.5)
	22	20.0%	(13.5,28.5)
135	14	10.4%	(6.2,16.8)
	21	15.6%	(10.3,22.7)
	27	20.0%	(14.1,27.6)
160	16	10.0%	(6.2,15.7)
	24	15.0%	(10.2,21.4)
	32	20.0%	(14.5,26.9)
170	17	10.0%	(6.3,15.5)
	26	15.3%	(10.6,21.5)
	34	20.0%	(14.6,26.7)
180	18	10.0%	(6.3,15.3)
	27	15.0%	(10.5,21.0)
	36	20.0%	(14.8,26.5)

ORR in PD-L1 strong (+) in Cohorts A + C

There will be ~55 subjects with PD-L1 strong (+) tumors enrolled in Cohort A and Cohort C.

Table 13 shows the two-sided 95% A-C CI of ORR with 55 evaluable subjects for different observed response rates. With 55 subjects with PD-L1 strong (+) tumors, if there are at least 11 responders observed, the lower bound of the 95% A-C CI for ORR will be above 10%.

Table 13 Two-sided 95% A-C CI of ORR with 55 Evaluable Subjects

Number of Observed Responders	ORR Estimates	95% A-C CI of ORR (%)
6	10.9%	(4.7,22.2)
8	14.5%	(7.3,26.4)
9	16.4%	(8.6,28.5)
10	18.2%	(10.0,30.5)
11	20.0%	(11.4,32.5)
13	23.6%	(14.2,36.5)
14	25.5%	(15.7,38.4)

Table 14 shows the Two-sided exact 95% CI of AE Rate with 55 subjects.

Table 14 Two-sided 95% Exact CI of AE Incidence Rate with 55 Evaluable Subjects

Number of AE	AE Incidence Rate Estimates	95% CI of Incidence Rate (%)
6	10.9%	(4.1,22.2)
11	20.0%	(10.4,33.0)
17	30.9%	(19.1,44.8)
22	40.0%	(27.0,54.1)
28	50.9%	(37.1,64.6)

ORR in PD-L1 (+) Cohort B

There will be ~80 subjects with PD-L1 (+) tumors enrolled in Cohort B.

Table 15 shows the two-sided 95% CI of ORR with 80 or 100 subjects for different observed response rates.

Table 15 Two-sided 95% A-C CI of ORR with 80 or 100 Subjects

Sample Size (N)	Number of Observed Responders	ORR Estimates	95% CI of ORR (%)
80	12	15%	(8.6,24.6)
	16	20%	(12.6,30.1)
	20	25%	(16.7,35.6)
	24	30%	(21.0,40.8)
	28	35%	(25.4,45.9)
	32	40%	(30.0,51.0)
	36	45%	(34.6,55.9)
100	15	15%	(9.2,23.4)
	20	20%	(13.3,29.0)
	25	25%	(17.5,34.4)
	30	30%	(21.9,39.6)
	35	35%	(26.3,44.8)
	40	40%	(30.9,49.8)
	45	45%	(35.6,54.8)

Table 16 shows the Two-sided exact 95% CI of AE Rate with 80 subjects.

Table 16 Two-sided 95% Exact CI of AE Incidence Rate with 80 Evaluable Subjects

Number of AE	AE Incidence Rate Estimates	95% CI of Incidence Rate (%)
8	10.0%	(4.4,18.8)
16	20.0%	(11.9,30.4)
24	30.0%	(20.3,41.3)
32	40.0%	(29.2,51.6)
40	50.0%	(38.6,61.4)

8.2.8 Subgroup Analyses and Effect of Baseline Factors

Subgroup analyses are planned for the efficacy analyses in the classification variables:

- Age category (≤ 50 vs. > 50 years)
- Menopausal status
- PD-L1 IHC expression [PD-L1 strong (+), PD-L1 (+), PD-L1 (-) and overall]
- Previous Chemotherapy (2/3 L vs. 4L+)
- Liver metastases (Presence vs. Absence)

8.2.9 Interim Analyses

[figure not shown]
There are two interim analyses planned in this study. For Cohort A in Part 1, a futility analysis will be performed for subjects with PD-L1 (-) tumors and an interim analysis for potential efficacy expansion will be performed for subjects with PD-L1 strong (+) tumors in this cohort.

The PD-L1 strong (+) population (10 or more subjects depending on the prevalence of PD-L1 strong (+) tumors in the 2L+ population from Cohort A) may be expanded by continuing enrollment of subjects with PD-L1 strong (+) tumors into Cohort C, if at least one responder is observed in this subpopulation from Cohort A. The combined sample size of up to ~55 subjects with PD-L1 strong (+) tumors from Cohorts A and C is driven by the primary efficacy estimation for subjects with PD-L1 strong (+) tumors (with futility bound accounted for the IA in this subpopulation).

The detailed process is described as below:

1. Enrollment will begin independent of tumor PD-L1 status.
2. A futility analysis will start when the first ~25 subjects with PD-L1 (-) tumors are evaluable through response, progression or 18-week tumor imaging, whichever comes first. The purpose of this interim analysis is to check treatment futility for subjects with PD-L1 (-) tumors.
3. If the futility boundary is not crossed, that is at least one subject with response or stable disease is observed in subjects with PD-L1 (-) tumors, the trial enrollment will continue as planned. If the futility boundary is crossed for subjects with PD-L1 (-) tumors, then such subjects may be excluded from further enrollment in the trial. That is, the trial will continue to only enroll subjects with PD-L1 (+) tumors until there are 160 subjects in total.
4. An efficacy futility interim will also be performed for the PD-L1 strong (+) subpopulation of Cohort A, and enrollment of Cohort C for PD-L1 strong (+) may be initiated if one or more responders are observed in at least 10 subjects from Cohort A.

Figure 4 illustrates the study diagram for decision making (a study decision tree).

[figure not shown]

Figure 4 Decision Tree

Interim Analysis for Futility (IA1)

An interim futility check will be performed for the PD-L1 (-) population in Cohort A. Enrollment of PD-L1 (-) population will be stopped, if futility bound is reached. At least one subject without disease progression among the 25 subjects is needed for the further enrollment of subjects with PD-L1 (-) tumors. [Table 17](#) lists the probability of stopping for futility at different true response rate in PD-L1 (-) based on different stopping rules.

Table 17 Probability of Futility under Different True Response Rate[§] in PD-L1 (-)

Response Rate [§] in PD-L1 (-)	Probability of Futility in PD-L1 (-)	
	Rule of ≥ 1 Responder or SD	Rule of ≥ 2 Responders or SD
1%	77.8%	97.4%
2%	60.3%	91.1%
5%	27.7%	64.2%
8%	12.4%	39.4%
10%	7.2%	27.1%

[§]Response rate: the proportion of responders (CR and PR) or subjects with stable disease.

Interim Analysis to Initiate Cohort C Expansion (IA 2)

IA2 (Cohort A) will be performed when at least 10 subjects with PD-L1 strong (+) tumors are evaluable through response, progression or 18-week scan, whichever comes first. One or more responses need to be observed in order to expand enrollment to additional subjects with PD-L1 strong (+) tumors (up to ~55 subjects in Cohorts A and C combined). [Table 18](#) shows the probability to initiate Cohort C under different true ORR in PD-L1 strong (+) subpopulation in Cohort A based on the rule of one or more responders.

Table 18 Probability to Initiate Cohort C under Different True ORR in PD-L1 Strong (+)

ORR in PD-L1 Strong (+)	Probability to Initiate Cohort C
10%	65.1%
15%	80.3%
18%	86.3%
20%	89.3%
25%	94.4%
30%	97.2%

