2.0 TRIAL DESIGN

2.1 Trial Design

Definitions

Line of treatment for metastatic triple-negative breast cancer (mTNBC):

Second line and above (2L+) monotherapy: for subjects with centrally confirmed mTNBC, who have received at least one systemic treatment for metastatic breast cancer and have documented disease progression on or after the most recent therapy. Subjects must have been previously treated with an anthracycline and a taxane in the (neo)adjuvant or metastatic setting.

First line (1L) monotherapy: for subjects with centrally confirmed PD-L1 (+) mTNBC, who have not received any prior systemic treatment for metastatic breast cancer.

Study cohorts:

Cohort A - Pembrolizumab as 2L+ monotherapy for mTNBC

Cohort B - Pembrolizumab as 1L monotherapy for PD-L1 (+) mTNBC

Cohort C - Expansion of the PD-L1 strong (+) subpopulation from Cohort A

This is a two-part, non-randomized, multi-site, open-label trial of pembrolizumab monotherapy in subjects with metastatic triple-negative breast cancer (mTNBC).

Part 1: Approximately 240 subjects will be enrolled in 2 cohorts, **Cohort A** (2L+ monotherapy for mTNBC independent of PD-L1 status, ~160 subjects) and **Cohort B** (1L monotherapy for PD-L1 (+) mTNBC, ~80 subjects) to examine the efficacy and safety of single agent pembrolizumab in the treatment of mTNBC. Cohorts A and B will be enrolled in parallel.

The relationship between response to treatment and PD-L1 protein expression in mTNBC will be explored in Cohort A. Furthermore, two interim analyses (IA 1 and 2) are planned for Cohort A.

First Interim Analysis: Subjects in Cohort A will initially be enrolled independent of tumor PD-L1 status. A futility analysis (Interim Analysis 1, IA 1) will be done on the PD-L1 (-) subpopulation of Cohort A to evaluate response in this group. If treatment with pembrolizumab is found to be futile in subjects with PD-L1 (-) tumors, then further enrollment in Cohort A will be limited to subjects with PD-L1 (+) tumors, including PD-L1 strong (+) tumors.

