sponsored multi-center, non-randomized Phase Ib trial (KN 012) showed that single agent pembrolizumab given at 10 mg/kg Q2W is a well-tolerated and effective treatment with significant therapeutic activity in a subset of heavily pre-treated patients with mTNBC.

Methods: PD-L1 expression in $\geq 1\%$ tumor cells or in stroma [i.e., PD-L1 (+) mTNBC] was required for study entry. Tumor PD-L1 status was determined by immunohistochemical analysis of archival tumor specimens using the Merck proprietary 22C3 antibody. Primary objectives of this study were to determine the safety, tolerability, and antitumor activity of pembrolizumab in patients with PD-L1 (+) mTNBC. Secondary objectives included assessments of progression-free survival (PFS), overall survival (OS), and duration of response (DOR). Adverse events (AEs) reported in any patient receiving at least 1 dose of study treatment were monitored and graded using National Cancer Institute Common Terminology Criteria for Adverse Events version 4.0 (NCI CTCAE v. 4.0). Radiographic imaging was obtained every 8 weeks and evaluated by both investigator and an independent radiologist to assess clinical responses as defined by RECIST 1.1.

Results: A total of 32 female patients with a median age of 50.5 years (range 29-72 years) and PD-L1 (+) mTNBC were enrolled in the study. Most of these patients had received and progressed on multiple lines of therapy for advanced disease (the median number of prior treatments in the metastatic setting was 3). According to data through 06-Nov-2014, five patients (15.6%) experienced at least one drug-related serious adverse event (SAE); each of four patients experienced one of the following: Grade 3 anemia, headache, aseptic meningitis or pyrexia, and a fifth patient experienced Grade 5 disseminated intravascular coagulation (DIC) with thrombocytopenia and decreased blood fibrinogen. Of the 27 patients with centrally confirmed measurable disease, one patient (3.7%) had a complete response (CR), 4 patients (14.8%) had a confirmed partial response (PR), 25.9% had stable disease (SD), and 44.4% had progressive disease (PD), as assessed by the central imaging vendor. As of 06-Nov-2014, the median duration of response had not been reached (range 15 to 40+ weeks), and three patients (1 CR; 2 PR) were still on treatment after at least 11 months.

KN 086: Subjects receiving pembrolizumab as 2L+ monotherapy for mTNBC (Cohorts A and C)

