8.1 Statistical Analysis Plan Summary

This section contains a brief summary of the statistical analyses for this trial. Full detail is in the Statistical Analysis Plan (SAP) (Section 8.2).

In addition, a separate analysis plan document will be issued prior to biomarker unblinding for each of the following laboratory procedures and assessments: (1) Biomarkers (detailed in Section 7.1.3.4 and 7.1.3.5) and their association with antitumor efficacy and (2) Pharmacokinetic and pharmacodynamics evaluation (detailed in Section 7.1.3.3)

Study Design Overview	A Phase II Clinical Trial of Pembrolizumab as Monotherapy in Subjects with Metastatic Triple-Negative Breast Cancer (mTNBC)
Treatment Assignment	Treatment assignment is open label.
Analysis Populations	Efficacy: All Subjects as Treated (ASaT) Safety: All Subjects as Treated (ASaT)
Primary Endpoint(s)	Objective Response Rate (ORR)
Statistical Methods for Key	ORR estimation

Efficacy Analyses	
 • 2L+ population 
 ○ PD-L1 (+) population (Cohort A) ○ Overall population (Cohort A) ○ PD-L1 strong (+) population (Cohorts A+C) • 1L population (Cohort B) • Counts and percentages • 95% Agresti-Coull confidence intervals
Statistical Methods for Key Safety Analyses	Counts and percentages of AEs will be provided. Confidence intervals for rates of AEs of clinical interest will be computed using the exact binomial method.
Interim Analyses	
 • Futility analysis for 2L+ subjects (Cohort A) with PD-L1 (-) tumors based on no progression 
 ○ ~25 PD-L1 (-) subjects ○ If no response or stable disease, continue 2L+ population (Cohort A) in PD-L1 (+) patients only • Evaluation of expansion to Cohort C for PD-L1 strong (+) population based on ORR. 
 ○ ~10 patients evaluable through response, progression or 18-week scan, whichever comes first. ○ Cohort C may start if ≥ 1 responses observed 
The final analysis of Cohorts A and C combined is to be completed when subjects are evaluable through response, progression or 18-week scan, whichever comes first.

Multiplicity	This is an estimation study. No multiplicity adjustment will be applied.

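### Is the first interim look too lenient because one stable disease among about 25 PD-L1 (-) subjects is enough to keep enrolling them?

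*Combined protocol and SAP*

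**What the plan says.** Protocol Section 8.2.9 schedules IA1 when the first 25 or so PD-L1 (-) subjects in Cohort A are "evaluable through response, progression or 18-week tumor imaging, whichever comes first". Enrolment of these subjects goes on if the boundary is not crossed, "that is at least one subject with response or stable disease is observed in subjects with PD-L1 (-) tumors". The IA1 paragraph repeats the rule in other words: "At least one subject without disease progression among the 25 subjects is needed for the further enrollment of subjects with PD-L1 (-) tumors". The Section 8.1 summary has the same basis: "Futility analysis for 2L+ subjects (Cohort A) with PD-L1 (-) tumors based on no progression".

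Table 17 gives the probability of stopping at rates of 1, 2, 5, 8 and 10%, and its footnote defines the rate: "Response rate: the proportion of responders (CR and PR) or subjects with stable disease". The sSAP repeats the rule and the table (Sections 3.1 and 3.7, Table 3).

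Two other places use response alone. Section 2.1 says that IA1 "will be done on the PD-L1 (-) subpopulation of Cohort A to evaluate response in this group". The second interim analysis, on PD-L1 strong (+) subjects, requires actual responses: "One or more responses need to be observed in order to expand enrollment to additional subjects with PD-L1 strong (+) tumors".

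**The concern.** A futility look is meant to stop when the treatment does nothing useful. Here a single subject with stable disease is enough to pass, so 25 subjects without one response can still be declared non-futile. Stable disease at 18 weeks is partly a matter of natural history, and the operating characteristics stop at a combined rate of 10%, below the figures the protocol reports for related settings.

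The verdict also has a use. Section 4.2.1 says that a non-futile result will lead to continued PD-L1 (-) enrolment in future studies, and to its consideration in later first-line studies. If the look can hardly fail, that verdict says little about response: 0 responses in 25 is compatible with a true ORR anywhere from 0 to 13.7% (exact 95% interval). The apparent remedy is to count only CR and PR, in line with Section 2.1, the primary endpoint and the second interim analysis.

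**Working it through.** **Inputs.** n = 25 and the rule of at least one CR, PR or SD (Section 8.2.9). Earlier phase Ib data in PD-L1 (+) mTNBC, 27 subjects with centrally confirmed measurable disease: "25.9% had stable disease (SD), and 44.4% had progressive disease (PD") (Section 4.2.1). Median PFS of 2-3 months on existing 2L+ therapy, and a median duration of third-line therapy of 4 weeks (Section 4.2.1). PD-L1 (-) NSCLC: ORR 9%, median time to response 14 weeks (Section 4.1.1). Expected PD-L1 (+) count 93 of 160 (Section 8.2.7). Section 4.2.1 states that there are no data for this drug in PD-L1 (-) mTNBC, so q has to be treated as unknown.

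**1. The plan's table.** P(stop) = (1-q)^25 gives 77.8, 60.3, 27.7, 12.4 and 7.2% at q = 1, 2, 5, 8 and 10%. This is the first column of Table 17. The column for at least two also reproduces.

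**2. Beyond the table.** P(stop) falls to 5% at q = 1 - 0.05^(1/25) = 11.3% (12.2% for n = 23, 10.5% for n = 27). At 15% it is 1.7% and at 20% it is 0.38%.

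**3. Where q might lie.**

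| Proxy | q | P(stop) |
|---|---|---|
| SD in PD-L1 (+) mTNBC, 7/27, no responses | 25.9% | 0.06% |
| Lower exact 95% limit of 7/27 | 11.1% | 5.3% |
| Median PFS 2 months, exponential, week 18 (4.14 months): 0.5^(4.14/2) | 23.8% | 0.11% |
| Median PFS 3 months, same form: 0.5^(4.14/3) | 38.4% | 0.0005% |
| Median third-line treatment 4 weeks, exponential: 0.5^(18/4) | 4.4% | about 32% |

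Most proxies lie above 11.3%, but none is the right quantity. The first is best response in PD-L1 (+) disease; Section 4.2.1 expects that PD-L1 (-) subjects may benefit less, and stability lasting to week 18 is rarer than stability at any scan. The last is duration of therapy, not PFS. The exponential form is an assumption throughout.

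**4. Which scan counts.** A subject becomes evaluable at response, at progression or at 18-week imaging. Stable disease at week 9 is none of these, and someone stable at week 9 who progresses by week 18 is a progressor. The rule therefore reads naturally as absence of progression at week 18, and the larger week-9 rates do not apply.

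**5. The alternative.** With responses only, the formula is the same and the rate becomes the ORR visible by week 18.

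| True ORR | P(stop), no CR or PR in 25 |
|---|---|
| 0% | 100% |
| 2% | 60.3% |
| 5% | 27.7% |
| 9% | 9.5% |
| 10% | 7.2% |

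If only 70-80% of eventual responses are visible by week 18 (an assumption), an eventual ORR of 10% gives (1-0.07)^25 = 16.3% to (1-0.08)^25 = 12.4%; if only half are visible, 27.7%. At an ORR of 5% the look still continues 100 - 27.7 = 72.3% of the time.

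**6. Subjects at stake.** If IA1 does not stop, 160 - 93 = 67 PD-L1 (-) subjects are expected, so 67 - 25 = 42 come after the first 25. The true figure is lower, because enrolment is not paused during IA1 (Section 2.2, Figure 1 footnote).

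**The case for a change.** The best argument for a change is that a drug no better than existing therapy would almost never cross this boundary: with a median PFS of 2-3 months, stopping has a probability of 0.11% or less. At a true ORR of zero, a response-only rule would always stop, while the present rule at an SD rate of 25.9% stops 0.06% of the time. The other rule in Table 17, at least two responders or SD, does not rescue it, stopping only 0.54% of the time at that rate. The edit would be short and need no extra subjects or scans.

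Much of this stands. The look is probably close to non-binding, and Table 17 does not show the range where that happens. What does not stand is that the alternative is plainly better. It would sharply separate only an ORR near 0-2% from the rest. At 9%, the ORR that Section 4.2.1 reports for capecitabine in TNBC, it would stop about one time in ten, and more often if responses are late. The plan expects late responses: Section 4.2.3.1 notes that they can follow an initial increase in tumor burden. The protocol states no futile or worthwhile ORR for PD-L1 (-) disease, so the documents give no basis for saying which error is worse. The interval of 0 to 13.7% also cuts both ways, because 0 of 25 is weak evidence for stopping too.

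The conflict with Section 2.1 is mild. The Figure 1 footnote in Section 2.2 ties exclusion to seeing no benefit, step 2 of Section 8.2.9 gives the purpose as checking futility, and DCR, a key secondary endpoint, counts stable disease of at least 24 weeks. Stable disease is part of what this plan means by benefit.

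Section 8.2.9 also uses permissive wording in step 3 and firm wording in the IA1 paragraph about what happens when the boundary is crossed. That is loose drafting, but it does not alter the calculation or the choice between the two rules.

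**Conclusion.** No change is needed; this is a fair trade-off. IA1 acts as a safeguard against near-universal progression in a group with few options and no prior data. It is stated the same way throughout the protocol and sSAP, and the table footnote discloses that stable disease is counted.

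The size of the weakness depends on an unknown q: 7.2% stopping at q = 10%, under 5% above 11.3%, about 0.1% or less at 24% and above. A response-only rule would exchange this for false stops of 9.5% at an ORR of 9% and 12.4-16.3% at an eventual 10% with some late responses, while still passing an ORR of 5% nearly three times in four. These figures assume independent subjects, n = 25 and status read by week 18.

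The consequences are limited. At most about 42 subjects are affected and no primary estimate is invalidated. Stopping more readily would leave fewer PD-L1 (-) subjects for the all-comers ORR and the PD-L1 association analysis. PD-L1 (-) response is estimated directly in the planned subgroup analysis (Section 8.2.8, sSAP 3.10), where 0 of 67 would bound the ORR at 5.4%, and in the biomarker analysis of response below each cut-off (sSAP 3.6.3). The plan does not offer the IA1 verdict as an estimate of response. Extending Table 17 to higher rates would inform the reader but change no decision or result.

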8.2.10 Compliance (Medication Adherence)

Drug accountability data for trial treatment will be collected during the study. Any deviation from protocol-directed administration will be reported.

8.2.11 Extent of Exposure

Extent of Exposure for a subject is defined as number of cycles in which the subject receives the study medication infusion. Summary statistics will be provided on Extent of Exposure for ASaT population.

8.2.12 Other Analyses

8.2.12.1 Biomarker Analyses

Biomarker endpoints including exploring the association between PD-L1 protein expression by IHC and response to pembrolizumab as monotherapy for mTNBC to define the biomarker cut-point for mTNBC will be analyzed in a separate SAP by biomarker group.

8.2.12.2 Other Exploratory Analysis

The association between LDH and efficacy response to pembrolizumab as monotherapy for mTNBC may be explored.

9.0 LABELING, PACKAGING, STORAGE AND RETURN OF CLINICAL SUPPLIES

9.1 Investigational Product

The investigator shall take responsibility for and shall take all steps to maintain appropriate records and ensure appropriate supply, storage, handling, distribution and usage of investigational product in accordance with the protocol and any applicable laws and regulations.

Clinical Supplies will be provided by the Sponsor as summarized in [Table 19](#).

Clinical supplies will be packaged to support enrollment and replacement subjects as required. When a replacement subject is required, the Sponsor or designee needs to be contacted prior to dosing the replacement supplies.

Table 19 Product Descriptions

Product Name & Potency	Dosage Form
pembrolizumab 100 mg / 4mL	Solution for Infusion

